4.1. Introduction

Data processing, tabulation of descriptive statistics, calculation of inferential statistics, and graphical representations will primarily use Statistical Analysis System Software (SAS) (release 9.4 or higher). If the use of other software is warranted, the final SAP and the statistical methodology report will detail what software was used for what purposes.

Continuous (quantitative) variable summaries will include the number of subjects (n) with non-missing values, mean, SD, median, minimum, and maximum. The minimum and maximum will be reported with the same degree of precision (i.e., the same number of decimal places) as the observed data. Measures of location (mean and median) will be reported to 1 degree of precision more than the observed data and measures of spread (SD) will be reported to 2 degrees of precision more than the observed data.

Categorical (qualitative) variable summaries will include the frequency and percentage of subjects who are in the category or each possible value. The denominator for the percentage calculation will be based upon the total number of subjects in the study population for the treatment groups unless otherwise specified. Percentages will be presented to 1 decimal place. Counts of zero will be presented without percentages.

Unless otherwise indicated, all statistical tests will be conducted at the 0.05 significance level using 2-tailed tests, and p values will be reported. Corresponding 95% confidence intervals (CIs) will be presented for statistical tests. All p values will be displayed in four decimals and rounded using standard scientific notation (e.g., 0.XXXX). If a p value less than 0.0001 occurs it will be shown in tables as < 0.0001 ; similarly, if a p value greater than 0.9999 occurs, it will be shown in tables as > 0.9999 . Confidence intervals will be reported to 1 degree of precision more than the observed data.

This study is considered a Phase 2a exploratory study under an IND application for PH94B targeting AjDA. Statistical tests will be applied and interpreted to determine feasibility and best approaches for potential Phase 2b and Phase 3 studies.

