4.2. Interim Analysis and Data Monitoring

No interim analyses or data monitoring are planned.

5. Analysis Populations

The following analysis populations are planned for this study:

- **All Subjects Population:** All subjects who sign an informed consent, participate in a Visit 1 (Screening), and are entered into the eCRF will be included in the All Subjects

population. The All Subjects population will be used for summaries of subject disposition.

- **Safety Population:** The Safety population includes all subjects who are dispensed IP and reported administering at least 1 dose of IP. The Safety population will be used for safety analyses. For analyses of the Safety population, each subject will be analyzed by the actual treatment received, even if it differs from the subject's randomized treatment assignment.
- **Intent-to-Treat (ITT) Population:** The ITT population includes all subjects who are randomized and have one documented dose of IP at Visit 2 (Baseline). The ITT population will be used for efficacy analyses. For analyses of the ITT population, each subject will be analyzed by their randomized treatment assignment, even if the subject did not receive the assigned treatment or did not follow the protocol until completion.

Assignment of subjects to populations will be confirmed at a blinded data review meeting to be held before the study database is locked. All protocol deviations that occur during the study will be considered for their severity/impact and will be taken into consideration when subjects are assigned to analysis populations.

6. General Issues for Statistical Analysis

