7.1. Disposition of Patients/Subjects and Withdrawals

Disposition will include tabulations of the number and percentage of subjects randomized into each treatment group, completing the study, and withdrawing from the study, along with reasons for withdrawal overall and by treatment group. Additionally, the number and percentage of subjects assigned to each analysis population will be displayed. Tabulations will be for all subjects and will be displayed by the planned treatment.

Additionally, inclusion and exclusion criteria not met will be listed for screen failures.

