14.2. Planned Table Shells

See [Figure 2](#) below.

Figure 2: Planned Table Shells

Table 14.1.1
 Subject Disposition
 All Subjects

Status Category	PH49B (N=XX)	Placebo (N=XX)	Overall (N=XX)
All Subjects Population [1]			
Screened for Eligibility			XX
Screen Failure at Visit 1 (Screening)			XX
Subject Failed to Return for Visit 2 (Baseline)			XX
Adverse Event			XX
Death			XX
Lost to Follow-Up			XX
Physician Decision			XX
Protocol Violation			XX
Withdrawal by Subject			XX
Study Terminated by Sponsor			XX
Disease Progression			XX
Other			XX
Screen Failure at Visit 2 (Baseline)			XX
Randomized	XX	XX	XX
Safety Population [1]	XX (XX.X%)	XX (XX.X%)	XX
ITT Population [2]	XX (XX.X%)	XX (XX.X%)	XX (XX.X%)

Abbreviation: ITT = intent-to-treat.

Note: Subjects are displayed by treatment received. Percentages are n/number of subjects in the Safety population within treatment received and overall subjects * 100.

[1] The All Subjects population includes all subjects who sign an informed consent, participate in Visit 1 (Screening), and are entered into the eCRF.

[2] The Safety population includes all subjects who were dispensed study drug and reported administering at least 1 dose.

[3] The ITT population includes all subjects who were randomized and had 1 documented dose of study drug at Visit 2 (Baseline).

Reference Listing: 16.2.1.1, 16.2.2.1, 16.2.3.1

Programming Note: Subjects who discontinue due to "Screen Failure" should not be included as a "Discontinued Early" subject. The "Ongoing in Study" row will only be presented for pre-lock blinded dry run deliveries; upon lock, it will be removed.

Table 14.1.1 (cont.)
Subject Disposition
All Subjects

Status Category	PH49B (N=xx)	Placebo (N=xx)	Overall (N=xx)
Completed Study	XX (XX.X%)	XX (XX.X%)	XX (XX.X%)
Ongoing in Study	XX (XX.X%)	XX (XX.X%)	XX (XX.X%)
Discontinued Early	XX (XX.X%)	XX (XX.X%)	XX (XX.X%)
Reason for Discontinuation:	XX (XX.X%)	XX (XX.X%)	XX (XX.X%)
Adverse Event	XX (XX.X%)	XX (XX.X%)	XX (XX.X%)
Death	XX (XX.X%)	XX (XX.X%)	XX (XX.X%)
Lack of Efficacy	XX (XX.X%)	XX (XX.X%)	XX (XX.X%)
Lost to Follow-Up	XX (XX.X%)	XX (XX.X%)	XX (XX.X%)
Non-Compliance with Study Drug	XX (XX.X%)	XX (XX.X%)	XX (XX.X%)
Physician Decision	XX (XX.X%)	XX (XX.X%)	XX (XX.X%)
Protocol Violation	XX (XX.X%)	XX (XX.X%)	XX (XX.X%)
Withdrawal by Subject	XX (XX.X%)	XX (XX.X%)	XX (XX.X%)
Study Terminated by Sponsor	XX (XX.X%)	XX (XX.X%)	XX (XX.X%)
Disease Progression	XX (XX.X%)	XX (XX.X%)	XX (XX.X%)

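### The disposition table shell groups subjects by treatment received over the Safety population, which contradicts SAP 7.1 and can misstate withdrawals by randomized arm

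*SAP*

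**What the plan says.** The SAP gives two rules for the same table.

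- **SAP 7.1 (text).** "Disposition will include tabulations of the number and percentage of subjects randomized into each treatment group, completing the study, and withdrawing from the study", with reasons for withdrawal. It adds that "the number and percentage of subjects assigned to each analysis population will be displayed", and fixes the layout: "Tabulations will be for all subjects and will be displayed by the planned treatment".
- **SAP Section 5.** "The All Subjects population will be used for summaries of subject disposition".
- **Table 14.1.1 shell (SAP 14.2).** The title names the All Subjects population, but the note on the first page and on the continuation page reads "Subjects are displayed by treatment received. Percentages are n/number of subjects in the Safety population within treatment received", and extends the same denominator to the Overall column. The Safety row carries a percentage in the two arm columns and a count only under Overall. The Randomized row carries counts only.

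On denominators in general, SAP 4.1 makes the size of the study population in each treatment group the default and allows a different one where the plan states it. SAP Section 11, which lists changes from the planned analysis, does not mention disposition.

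**The concern.** The columns of a disposition table should show what happened to the people randomized to each arm. Grouping by treatment received and dividing by those who took a dose builds a post-randomization condition into both the numerator and the denominator. A subject lost between randomization and first dose has no treatment received and so has no arm column. A subject given the wrong product moves to the other arm, even in the row that counts randomized subjects. The percentage that SAP 7.1 requires for the Safety population becomes a ratio of a number to itself.

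At stake is the summary of withdrawals, across all reasons, by randomized arm. The ITT population also requires a documented dose at Visit 2, so an undosed subject is outside both the efficacy and the safety tables. Disposition is the one summary table where that loss and its reason could appear by arm.

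**Working it through.** The plan states no figure to reproduce. The check is definitional, followed by simple proportions.

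**Inputs from the documents**
- Planned size: 40 subjects randomized 1:1, so about 20 per arm (Protocol synopsis).
- Safety population: "The Safety population includes all subjects who are dispensed IP and reported administering at least 1 dose of IP" (SAP Section 5). Undosed subjects are outside it.
- Subjects with no dose are foreseen: the Listing 16.2.3.1 shell has an example row with a randomization date and number that is neither Safety nor ITT.
- Dosing errors are foreseen: Protocol 13.1.1 says how to analyze subjects given the incorrect product.

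**Assumed for illustration**
- k subjects randomized to PH94B withdraw undosed, and two dosed subjects withdraw in each arm. The documents give no figure for either.

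**Step 1, the Safety row.** In an arm column the shell computes n(Safety, received arm) / n(Safety, received arm) = 100.0%, whatever the data.

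**Step 2, undosed subjects, reading the note literally.** Shell rule for PH94B withdrawals: 2 / (20 − k). By planned arm over the number randomized: (2 + k) / 20. The shell's Overall column takes (4 + k) / (40 − k), if undosed subjects are counted there.

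| k | Safety row, PH94B: shell | by planned arm | Discontinued, PH94B: shell | by planned arm | Discontinued, Overall: shell | over randomized |
|---|---|---|---|---|---|---|
| 0 | 20/20 = 100.0% | 20/20 = 100.0% | 2/20 = 10.0% | 2/20 = 10.0% | 4/40 = 10.0% | 4/40 = 10.0% |
| 1 | 19/19 = 100.0% | 19/20 = 95.0% | 2/19 = 10.5% | 3/20 = 15.0% | 5/39 = 12.8% | 5/40 = 12.5% |
| 2 | 18/18 = 100.0% | 18/20 = 90.0% | 2/18 = 11.1% | 4/20 = 20.0% | 6/38 = 15.8% | 6/40 = 15.0% |
| 3 | 17/17 = 100.0% | 17/20 = 85.0% | 2/17 = 11.8% | 5/20 = 25.0% | 7/37 = 18.9% | 7/40 = 17.5% |

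With one undosed withdrawal and only one later withdrawal in the arm, the shell gives 1/19 = 5.3%, against 2/20 = 10.0% by planned arm.

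The table also stops adding up. At k = 2 the Randomized row reads 18 + 20 = 38 by arm against 40 overall. The arm withdrawals sum to 2 + 2 = 4 against 6 overall. Overall completed plus discontinued is 40/38 = 105.3%.

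**Step 3, a misdosed subject.** If one placebo-randomized subject receives PH94B and nobody is undosed, the Randomized row reads 20 + 1 = 21 and 20 − 1 = 19 instead of 20 and 20. Two withdrawals in each column then read 2/21 = 9.5% and 2/19 = 10.5% instead of 10.0% in both.

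**Step 4, no such subject.** With k = 0 and no dosing error, the two rules give identical figures in every row.

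**The case against.** The strongest reply is that this is a descriptive footnote with little practical reach, and much of that stands.

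- **The trigger is unlikely.** Eligibility is settled before randomization at Visit 2, and the first dose is taken at that visit in front of site staff (Protocol 9 and 10.2.2). Few subjects, perhaps none, will be randomized and undosed.
- **The effect on the Randomized row is an inference.** The shell does not say where a subject with no treatment received belongs, and that row has no percentage. Programmed from the randomization record, it could show 20 against a Safety count of 19, and the loss would be visible. The literal note points the other way, but the outcome is not certain.
- **The denominator conflict is less direct than the grouping conflict.** SAP 4.1 allows a specified alternative and SAP 7.1 names none. A reader might infer that 7.1 demands the number randomized; it does not.
- **The 100% result is confined to the arm columns.** The Overall Safety cell has no percentage.

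A reader might also infer that the shell hides missing data in the primary analysis. The documents do not support that. The primary analysis and its missing fraction are defined on ITT subjects (SAP 6.1.7.2 and 8.1), and undosed subjects are not in ITT. Nor is this the only view of attrition by arm: Table 14.2.1.1 gives the ITT N and the observed n at Visits 3 to 6 by planned treatment. It would also be too strong to say that the table cannot reconcile with the efficacy tables, since a mismatch from this cause needs at least one undosed or misdosed subject. Listing 16.2.3.1, sorted by planned treatment, would let such a subject be traced.

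None of this removes the contradiction between SAP 7.1 and the shell over which treatment defines the columns.

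**Conclusion.** The inconsistency is real and explicit: the text prescribes planned treatment, and the shell prescribes treatment received. The Safety denominator also sits badly with the All Subjects population that SAP Section 5 assigns to disposition, and it makes the arm-level Safety percentage uninformative by construction.

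The size depends on events the documents do not quantify. In the illustration, each undosed withdrawal removes one subject from the arm's withdrawal count and one from its denominator, so at 20 per arm the reported rate falls short by about 4 to 5 percentage points for one such subject (5.3% against 10.0%, or 10.5% against 15.0%). With no undosed and no misdosed subject, the difference is zero. No estimate, test or analysis population changes under any scenario. This is a minor reporting correction, worth making because Table 14.1.1 is the only summary table that sets out withdrawals across all reasons.

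**What to change.** Rewrite the note on both pages of the Table 14.1.1 shell so that the columns are the randomized (planned) arms, as SAP 7.1 requires. For rows after randomization, use the number randomized to the arm as denominator, and all randomized subjects under Overall. State that denominator in SAP 7.1 as well, so that text and shell agree.

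There is one small downside. If anyone is misdosed, the Safety count by planned arm will differ from the N in the safety tables, which are by actual treatment. A one-line footnote should say so.

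While the shell is open, align its bracketed markers with the legend: the Safety and ITT rows carry [1] and [2], but their definitions are numbered [2] and [3].

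The cost is one footnote, one grouping variable and one denominator in a single table program, with no new data and no effect on any analysis.

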6.1.4. Handling of Dropouts or Missing Data

Data will be included in the analysis according to the analysis visit windows described in Section 6.1.5.

Treatment of intercurrent events (ICEs) will be as described in Table 3. Briefly, subjects who withdraw from the study after treatment begins will be encouraged to complete an Early Termination Visit where all Visit 6 assessments will be performed. If the subject is lost to follow-up or otherwise unable to complete the Visit 6 assessments or if the subject uses a prohibited medication prior to the planned end of treatment, the Visit 6 HAM-A score will be set to missing. If the fraction of missing change from baseline to Visit 6 HAM-A total scores in the ITT population is ≤ 0.05 , missing change scores will be imputed with treatment group mean change scores for the primary efficacy analysis. If the fraction of missing change scores is greater than 0.05, multiple imputation of the change from baseline to Visit 6 HAM-A total scores will be carried out for the primary efficacy analysis. The fraction of missing change from baseline to Visit 6 HAM-A total scores will be computed as described in Section 6.1.7.2. The multiple imputation procedure will not impute individual HAM-A item scores or HAM-A total scores; only change from baseline to Visit 6 HAM-A total scores will be imputed. Other efficacy and safety data will not be imputed and will be analyzed as observed.

Table 3: Strategies for Intercurrent Events

ICE	Strategy for Addressing ICE
Treatment discontinuation following randomization but prior to Week 4.	While on Treatment Strategy The research objectives seek to understand the response to PH94B compared to placebo while subjects are actively using the study medication. Subjects who discontinue will undergo an Early Termination Visit and provide all Visit 6 outcome measures and safety assessments for the efficacy analysis.

ICE	Strategy for Addressing ICE

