9.7. Columbia-Suicide Severity Rating Scale (C-SSRS)

The number and percentage of subjects reporting "Yes" for any of the 5 suicidal ideation questions (Categories 1 to 5) or any of the 5 suicidal behavior questions (Categories 6 to 10) will be displayed for each treatment group and overall subjects, along with the number and percentage reporting suicidal ideation OR behavior (Categories 1 to 10). The number and percentage of subjects with treatment emergent suicidal ideation, treatment emergent suicidal behavior, and treatment emergent suicidal ideation or behavior as defined in Section 6.1.7.9 will also be presented.

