Abbreviations: ECG = electrocardiogram; QTcF = QT interval, Fridericia's correction.
Note: Percentages are n/Number of subjects in the Safety population at each study visit within treatment received and overall subjects * 100. Change from baseline is calculated as result – baseline result.
[1] Visit 6 (End of Treatment/Early Termination) includes data from subjects who either completed Visit 6 (End of Treatment) or who discontinued from the study and completed an early termination visit.
[2] Baseline is defined as the last non-missing assessment before receiving the first dose of study drug.
Reference Listing: 16.2.9.2

Table 14.3.6.3
Summary of Concomitant Medications by ATC Class Level 2 and Preferred Term
Safety Population

*Same shell as 14.1.5 except first row text is "Subjects with at least 1 Concomitant Medication"; Programming Note: Update note to read: "Percentages are n/Number of subjects in the Safety population within treatment received and overall subjects * 100. Concomitant medications are any medications starting or continuing after Visit 2 (Baseline). Medications were coded using WHO-DD Global B3 version XX. At each level of summarization (ATC Level 2 or PT), subjects who reported more than one medication were only counted once. Medications are displayed by alphabetical order of ATC Level 2 classification, then descending frequency of PT within ATC, and then alphabetically by PT. Subjects were counted only once for each ATC and PT." Update Reference Listing to Listing 16.2.9.4. Replace "XX" in the footnote with the correct version of the WHO-DD used for coding. For dry run delivery, use WHO-DD Global B3 version Sep 2021.*

[figure not shown]

Table 14.3.6.4
Summary of Columbia Suicide Severity Rating Scale (C-SSRS) by Visit
Safety Population

Study Visit [1] C-SSRS Section C-SSRS Item / Statistic	PH94B (N=XX)	Placebo (N=XX)	Overall (N=XX)
Visit 1 (Screening)			
Suicidal Ideation: Last 6 Months	XX (XX.X%)	XX (XX.X%)	XX (XX.X%)
Wish to be Dead	XX (XX.X%)	XX (XX.X%)	XX (XX.X%)
Non-Specific Active Suicidal Thoughts	XX (XX.X%)	XX (XX.X%)	XX (XX.X%)
Active Suicidal Ideation with Any Methods	XX (XX.X%)	XX (XX.X%)	XX (XX.X%)
Active Suicidal Ideation with Some Intent	XX (XX.X%)	XX (XX.X%)	XX (XX.X%)
Active Suicidal Ideation with Specific Plan	XX (XX.X%)	XX (XX.X%)	XX (XX.X%)
Suicidal Behavior: Lifetime	XX (XX.X%)	XX (XX.X%)	XX (XX.X%)
Actual Attempt	XX (XX.X%)	XX (XX.X%)	XX (XX.X%)
Interrupted Attempt	XX (XX.X%)	XX (XX.X%)	XX (XX.X%)

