Aborted Attempt	XX (XX.X%)	XX (XX.X%)	XX (XX.X%)
Preparatory Acts or Behavior	XX (XX.X%)	XX (XX.X%)	XX (XX.X%)
Suicidal Ideation or Behavior			
Subject Engaged in Non-Suicidal Self-Injurious Behavior	XX (XX.X%)	XX (XX.X%)	XX (XX.X%)

Abbreviation: C-SSRS = Columbia Suicide Severity Rating Scale.

Note: Percentages are n/Number of subjects in the Safety population within treatment received and overall subjects * 100. The number and percent of subjects who experience the event at least once during treatment are summarized. Subjects were counted once for each C-SSRS section and once for each C-SSRS item answered "Yes" during treatment period. "Baseline/Screening" version was used for Visit 1 (Screening) and "Since Last Visit" was used for all other visits.

[1] Visit 6 (End of Treatment/Early Termination) includes data from subjects who either completed Visit 6 (End of Treatment) or who discontinued from the study and completed an early termination visit.

[2] Subjects are considered to have treatment emergent suicidal ideation if their maximum suicidal ideation score increased from a previous visit to the next visit after treatment with study drug.

[3] Subjects are considered to have treatment emergent suicidal behavior if they did not have suicidal behavior prior to treatment with study drug but did have suicidal behavior at any visit after treatment with study drug.

Reference Listings: 16.2.9.5

Programming Note: Display summaries for all visits, including Visit 1 (Screening), Visit 2 (Baseline), Visit 3, Visit 4, Visit 5, Visit 6 (End of Treatment/Early Termination), Visit 7 (Follow-Up). Present treatment emergent counts and percentages as the last lines in the table after Visit 7 (Follow-Up).

[figure not shown]

Table 14.3.6.4 (cont.)
Summary of Columbia Suicide Severity Rating Scale (C-SSRS) by Visit
Safety Population

Study Visit [1] C-SSRS Section C-SSRS Item / Statistic	PH94B (N=XX)	Placebo (N=XX)	Overall (N=XX)
Visit 2 (Baseline)			
Suicidal Ideation: Since Last Visit	XX (XX.X%)	XX (XX.X%)	XX (XX.X%)
Wish to be Dead	XX (XX.X%)	XX (XX.X%)	XX (XX.X%)
Non-Specific Active Suicidal Thoughts	XX (XX.X%)	XX (XX.X%)	XX (XX.X%)
Active Suicidal Ideation with Any Methods	XX (XX.X%)	XX (XX.X%)	XX (XX.X%)
Active Suicidal Ideation with Some Intent	XX (XX.X%)	XX (XX.X%)	XX (XX.X%)
Active Suicidal Ideation with Specific Plan	XX (XX.X%)	XX (XX.X%)	XX (XX.X%)
Suicidal Behavior: Since Last Visit	XX (XX.X%)	XX (XX.X%)	XX (XX.X%)

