Suicidal Behavior: Since Last Visit	XX (XX.X%)	XX (XX.X%)	XX (XX.X%)
Completed Suicide	XX (XX.X%)	XX (XX.X%)	XX (XX.X%)
Actual Attempt	XX (XX.X%)	XX (XX.X%)	XX (XX.X%)
Interrupted Attempt	XX (XX.X%)	XX (XX.X%)	XX (XX.X%)
Aborted Attempt	XX (XX.X%)	XX (XX.X%)	XX (XX.X%)
Preparatory Acts or Behavior	XX (XX.X%)	XX (XX.X%)	XX (XX.X%)
Suicidal Ideation or Behavior	XX (XX.X%)	XX (XX.X%)	XX (XX.X%)
Subject Engaged in Non-Suicidal Self-Injurious Behavior	XX (XX.X%)	XX (XX.X%)	XX (XX.X%)
Treatment Emergent Suicidal Ideation [2]	XX (XX.X%)	XX (XX.X%)	XX (XX.X%)
Treatment Emergent Suicidal Behavior [3]	XX (XX.X%)	XX (XX.X%)	XX (XX.X%)
Treatment Emergent Suicidal Ideation or Behavior	XX (XX.X%)	XX (XX.X%)	XX (XX.X%)

Abbreviation: C-SSRS = Columbia Suicide Severity Rating Scale.

Note: Percentages are n/Number of subjects in the Safety population within treatment received and overall subjects * 100. The number and percent of subjects who experience the event at least once are summarized. Subjects were counted once for each C-SSRS section and once for each C-SSRS item answered "Yes" during treatment period. "Baseline/Screening" version was used for Visit 1 (Screening) and "Since Last Visit" was used for all other visits.

[1] Visit 6 (End of Treatment/Early Termination) includes data from subjects who either completed Visit 6 (End of Treatment) or who discontinued from the study and completed an early termination visit.

[2] Subjects are considered to have treatment emergent suicidal ideation if their maximum suicidal ideation score increased from a previous visit to the next visit after treatment with study drug.

[3] Subjects are considered to have treatment emergent suicidal behavior if they did not have suicidal behavior prior to treatment with study drug but did have suicidal behavior at any visit after treatment with study drug.

Reference Listings: 16.2.9.5

Programming Note: Display summaries for all visits, including Visit 1 (Screening), Visit 2 (Baseline), Visit 3, Visit 4, Visit 5, Visit 6 (End of Treatment/Early Termination), Visit 7 (Follow-Up). Present treatment emergent counts and percentages as the last lines in the table after Visit 7 (Follow-Up).

AD-ST-33.06 Effective date: 12-Nov-2020

[figure not shown]

Table 14.3.6.5
Summary of Montgomery-Asberg Depression Rating Scale (MADRS) Total Score by Visit
Safety Population

Study Visit [1] Statistic	PH94B (N=XX)		Placebo (N=XX)		Overall (N=XX)	
	Observed	CFB	Observed	CFB	Observed	CFB

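### The by-visit C-SSRS table divides by the whole Safety population, so percentages at Visits 3 to 7 fall below the rate among subjects assessed whenever assessments are missed

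*SAP*

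**What the plan says.** Each shell page of SAP Table 14.3.6.4 (Section 14.2) carries the same rule: "Percentages are n/Number of subjects in the Safety population within treatment received and overall subjects * 100". The programming note asks for a block per visit: "Display summaries for all visits, including Visit 1 (Screening), Visit 2 (Baseline), Visit 3, Visit 4, Visit 5", continuing to Visits 6 and 7. The treatment-emergent rows close the table. The ideation and behavior items appear only as counts of subjects answering yes. There is no row for the number assessed and no Missing row.

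SAP Section 9.7 says that the results "will be displayed for each treatment group and overall subjects, along with the number and percentage reporting suicidal ideation OR behavior"; it names no denominator and no rule for a missed assessment. The general default in Section 4.1 is that percentages are "based upon the total number of subjects in the study population for the treatment groups unless otherwise specified".

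Three other places bear on this:

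- SAP Section 6.1.4, after describing the imputation of HAM-A: "Other efficacy and safety data will not be imputed and will be analyzed as observed".
- The note to the QT/QTcF table (14.3.6.2.3), another by-visit safety table: "Percentages are n/Number of subjects in the Safety population at each study visit within treatment received and overall subjects * 100". That shell also prints n at each visit.
- SAP Section 5: "The Safety population includes all subjects who are dispensed IP and reported administering at least 1 dose of IP". One dose is enough, so the population includes subjects who later miss visits or leave.

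**The concern.** A subject with no C-SSRS at a visit cannot enter the numerator for that visit but stays in the denominator. The percentage then depends on attendance as well as on suicidality. If attendance differs between arms, the arm with more missed assessments shows the lower percentage for the same rate among those assessed.

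Change in suicidal ideation is a named safety endpoint (SAP Section 2.2.2). With about 20 subjects per arm, one subject is 5 percentage points, so readers will be comparing very small counts. A difference produced by attendance would be hard to see, because the table gives no sign of how many subjects were assessed.

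**Working it through.** **Inputs from the documents.** Forty subjects randomized 1:1 (Protocol synopsis), so about N = 20 per arm. Withdrawn subjects are not replaced (Protocol Section 8.4), so the number assessed can fall below N. Missed C-SSRS assessments are foreseen: Listing 16.2.9.5 has a field for the reason.

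**Assumed inputs.** The documents give no dropout rate and no ideation or behavior rate. The event counts x and numbers assessed n below are assumptions. There is no plan figure to reproduce.

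**Formulas.**

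- Printed percentage = 100 × x / N(Safety)
- Percentage among assessed = 100 × x / n(assessed)
- Printed / assessed = n(assessed) / N(Safety)

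**One arm, N = 20, x = 2.** Printed = 100 × 2/20 = 10.0%, whatever the attendance.

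| n assessed | Among assessed | Printed / assessed |
|---|---|---|
| 20 | 2/20 = 10.0% | 1.00 |
| 19 | 2/19 = 10.5% | 0.95 |
| 18 | 2/18 = 11.1% | 0.90 |
| 17 | 2/17 = 11.8% | 0.85 |
| 16 | 2/16 = 12.5% | 0.80 |
| 14 | 2/14 = 14.3% | 0.70 |

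**Two arms with unequal attendance.** Suppose 3 of 15 assessed subjects answer yes in one arm and 4 of 20 in the other. Among those assessed, both rates are 20.0%. The table prints 3/20 = 15.0% and 4/20 = 20.0%. The 5-point gap comes from attendance alone.

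**Which visits are exposed.**

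- Visits 1 and 2: the C-SSRS feeds exclusion criterion 6 and precedes the first dose, so nearly every Safety subject should have it.
- Visits 3 to 5: exposed to early leavers and missed visits.
- Visit 6: the shell's visit footnote includes early-termination assessments, which narrows the gap.
- Visit 7: exposed. It is also the only scheduled C-SSRS after the 1-week washout, and no later scheduled visit can pick up what it misses.

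**Comparison with neighbouring shells.** The ECG interpretation table (14.3.6.2.1) uses the same whole-population note, but its three categories are exhaustive, so they add up to the number assessed. The CGI-I shell (14.2.2.1) prints a Missing row. The C-SSRS table prints only yes rows, so the number assessed cannot be worked out from it.

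**The case against.** The strongest reply is that this is the SAP's chosen rule. Section 4.1 makes the whole population the default, and the ECG interpretation and CGI-I shells follow it. The QT note does not literally say assessed either. That shows the denominator is deliberate, but not that it gives a sound by-visit rate. Those two shells let the reader see who is missing, and this one does not.

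Other points on that side stand and limit the finding:

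- **Recoverability.** A reader might infer that the information is lost. It is not. Counts and column N are printed, Listing 16.2.9.5 shows by visit whether the C-SSRS was completed, and the vital-signs n in Table 14.3.6.1 is a rough guide to attendance. The number assessed is missing from this table, not from the report.
- **Treatment-emergent rows.** A reader might extend the criticism to these. They are cumulative over the study, and the Safety N matches the treatment-emergent adverse event tables, so that denominator is defensible.
- **Classification as event-free.** A reader might infer that the SAP counts unassessed subjects as free of ideation. It never says so; the table has no row for a no answer. The effect is arithmetical. In addition, the since-last-visit version means that a later completed assessment can capture an event from a missed visit, though under the later visit's block.
- **Attendance after discontinuation.** Protocol Section 8.3 asks subjects who stop early to return for scheduled weekly assessments or, failing that, to complete Visit 6 assessments, which limits the shortfall.
- **Informative dropout.** If subjects leave because they are doing badly, dividing by those assessed still omits them.
- **Stakes.** The table is descriptive and untested, and is produced after database lock. The absence of a monitoring board and the suicide rate cited in the protocol's background do not make it a subject-protection issue.

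**Conclusion.** The point holds for the by-visit rows. At Visits 3 to 7, and mainly at 3 to 5 and 7, the printed percentage is the rate among assessed subjects multiplied by n(assessed)/N(Safety). The two agree only if every Safety subject is assessed or there are no events. Otherwise the printed figure is too low and, in relative terms, more so in the arm with more missed assessments. That does not fit the SAP's statement that safety data are analyzed as observed, nor its handling of the QT table.

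The relative understatement is 5% with 1 of 20 not assessed and 20% with 4 of 20 not assessed. Those attendance figures are assumptions, and the documents allow no estimate of the actual effect. A reading that every visit is distorted, or that the treatment-emergent results are wrong, goes beyond what the documents support. This is a reporting defect that should be corrected because the remedy is nearly free.

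**What to change.** In Table 14.3.6.4:

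1. For the by-visit rows, replace the percentage note with: *Percentages are based on Safety subjects with a C-SSRS at that visit.* Section 4.1 allows such an exception where it is specified.
2. Print that n as the first row of each visit block, by arm and overall.
3. For the three treatment-emergent rows, keep the Safety N, say so in the note, and add one row with the number of Safety subjects who have no post-dose C-SSRS.

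The cost is a revised note, one row in each of the seven visit blocks and one row at the end. No new data are needed. By-visit percentages stay the same or rise. The change makes them as-observed rates that can be read with their denominators; unequal or informative dropout must still be considered when they are interpreted.
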